16.3.3.2.10 Sensitivity analysis

This section outlines the possible event and censoring dates for progression, as well as addresses the issues of missing tumor assessments during the study. For instance, if one or more assessment visits are missed prior to the progression event, to what date should the progression event be assigned? And should progression event be ignored if it occurred after a long period

of a subject being lost to follow-up? It is important that the protocol and RAP specify the primary analysis in detail with respect to the definition of event and censoring dates and also include a description of one or more sensitivity analyses to be performed.

Based on definitions outlined in [Section 16.3.3.2.8](#), and using the FDA guideline on endpoints ([Section 16.3.5](#)) as a reference, the following analyses can be considered:

Table 16-7 Options for event dates used in PFS, TTP, duration of response

Situation		Options for end-date (progression or censoring)¹ (1) = default unless specified differently in the protocol or RAP	Outcome
A	No baseline assessment	(1) Date of randomization/start of treatment ³	Censored
B	Progression at or before next scheduled assessment	(1) Date of progression (2) Date of next scheduled assessment ²	Progressed Progressed
C1	Progression or death after exactly one missing assessment	(1) Date of progression (or death) (2) Date of next scheduled assessment ²	Progressed Progressed
C2	Progression or death after two or more missing assessments	(1) Date of last adequate assessment ² (2) Date of next scheduled assessment ² (3) Date of progression (or death)	Censored Progressed Progressed
D	No progression	(1) Date of last adequate assessment	Censored
E	Treatment discontinuation due to 'Disease progression' without documented progression, i.e. clinical progression based on investigator claim	(1) Ignore clinical progression and follow situations above (2) Date of discontinuation (visit date at which clinical progression was determined)	As per above situations Progressed
F	New anticancer therapy given	(1) Ignore the new anticancer therapy and follow situations above (ITT approach)	As per above situations Censored Censored Event

Situation	Options for end-date (progression or censoring) ¹ (1) = default unless specified differently in the protocol or RAP	Outcome
	(2) Date of last adequate assessment prior to new anticancer therapy (3) Date of secondary anti-cancer therapy (4) Date of secondary anti-cancer therapy	
G	Deaths due to reason other than deterioration of 'Study indication'	(1) Date of last adequate assessment

1 =Definitions can be found in [Section 16.3.3.2.8](#)

2 =After the last adequate tumor assessment. "Date of next scheduled assessment" is defined in [Section 16.3.3.2.8](#).

3 =The rare exception to this is if the subject dies no later than the time of the second scheduled assessment as defined in the protocol in which case this is a PFS event at the date of death.

The primary analysis and the sensitivity analyses must be specified in the protocol. Clearly define if and why options (1) are not used for situations C, E and (if applicable) F.

Situations C (C1 and C2): Progression or death after one or more missing assessments: The primary analysis is usually using options (1) for situations C1 and C2, i.e.

- (C1) taking the actual progression or death date, in the case of only one missing assessment.
- (C2) censoring at the date of the last adequate assessment, in the case of two or more consecutive missing assessments.

In the case of two or missing assessments (situation C2), option (3) may be considered jointly with option (1) in situation C1 as sensitivity analysis. A variant of this sensitivity analysis consists of backdating the date of event to the next scheduled assessment as proposed with option (2) in situations C1 and C2.

Situation E: Treatment discontinuation due to 'Disease progression' without documented progression: By default, option (1) is used for situation E as subjects without documented PD should be followed for progression after discontinuation of treatment. However, option (2) may be used as sensitivity analysis. If progression is claimed based on clinical deterioration instead of tumor assessment by e.g. CT scan, option (2) may be used for indications with high early progression rate or difficulties to assess the tumor due to clinical deterioration.

Situation F: New cancer therapy given: the handling of this situation must be specified in detail in the protocol. However, option (1) (ITT) is the recommended approach; events documented after the initiation of new cancer therapy will be considered for the primary

analysis i.e. progressions and deaths documented after the initiation of new cancer therapy would be included as events. This will require continued follow-up for progression after the start of the new cancer therapy. In such cases, it is recommended that an additional sensitivity analysis be performed by censoring at last adequate assessment prior to initiation of new cancer therapy.

Option (2), i.e. censoring at last adequate assessment may be used as a sensitivity analysis. If a high censoring rate due to start of new cancer therapy is expected, a window of approximately 8 weeks performed after the start of new cancer therapy can be used to calculate the date of the event or censoring. This should be clearly specified in the analysis plan.

In some specific settings, local treatments (e.g. radiation/surgery) may not be considered as cancer therapies for assessment of event/censoring in PFS/TPP/DoR analysis. For example, palliative radiotherapy given in the trial for analgesic purposes or for lytic lesions at risk of fracture will not be considered as cancer therapy for the assessment of BOR and PFS analyses. The protocol should clearly state the local treatments which are not considered as antineoplastic therapies in the PFS/TPP/DoR analysis.

The protocol should state that tumor assessments will be performed every x weeks until radiological progression irrespective of initiation of new antineoplastic therapy. It is strongly recommended that a tumor assessment is performed before the subject is switched to a new cancer therapy.

Additional suggestions for sensitivity analyses

Other suggestions for additional sensitivity analyses may include analyses to check for potential bias in follow-up schedules for tumor assessments, e.g. by assigning the dates for censoring and events only at scheduled visit dates. The latter could be handled by replacing in [Table 16-7](#) the “Date of last adequate assessment” by the “Date of previous scheduled assessment (from baseline)”, with the following definition:

- **Date of previous scheduled assessment (from baseline)** is the date when a tumor assessment would have taken place, if the protocol assessment scheme was strictly followed from baseline, immediately before or on the date of the last adequate tumor assessment.

In addition, analyses could be repeated using the Investigators’ assessments of response rather than the calculated response. The need for these types of sensitivity analyses will depend on the individual requirements for the specific study and disease area and have to be specified in the protocol or RAP documentation.

16.3.4 Data handling and programming rules

The following section should be used as guidance for development of the protocol, data handling procedures or programming requirements (e.g. on incomplete dates).

16.3.4.1 Study / project specific decisions

For each study (or project) various issues need to be addressed and specified in the protocol or RAP documentation. Any deviations from protocol must be discussed and defined at the latest in the RAP documentation.

The proposed primary analysis and potential sensitivity analyses should be discussed and agreed with the health authorities and documented in the protocol (or at the latest in the RAP documentation before database lock).

16.3.4.2 End of treatment phase completion

Subjects **may** voluntarily withdraw from the study treatment or may be taken off the study treatment at the discretion of the investigator at any time. For subjects who are lost to follow-up, the investigator or designee should show "due diligence" by documenting in the source documents steps taken to contact the subject, e.g., dates of telephone calls, registered letters, etc.

The EOT visit and its associated assessments should occur within 21 days of the permanent discontinuation of study treatment but before the surgery.

Subjects may discontinue study treatment for any of the following reasons:

- AE(s)
- Lost to follow-up
- Physician decision
- Pregnancy
- Protocol deviation
- Technical problems
- Subject/guardian decision
- Progressive disease
- Study terminated by the sponsor
- Non-compliant with study treatment
- No longer requires treatment
- Treatment duration completed as per protocol (optional, to be used if only a fixed number of cycles is given)

Death is a reason which "*must*" lead to discontinuation of subject from trial.

16.3.4.3 End of post-treatment follow-up (study phase completion)

End of post-treatment follow-up visit will be completed after discontinuation of study treatment and post-treatment evaluations but prior to collecting survival follow-up.

Subjects may provide study phase completion information for one of the following reasons:

- AE
- Lost to follow-up
- Physician decision
- Pregnancy
- Protocol deviation
- Technical problems
- Subject/guardian decision

- Death
- Progressive disease
- Study terminated by the sponsor

16.3.4.4 Medical validation of programmed overall lesion response

In order to be as objective as possible the RECIST programmed calculated response assessment is very strict regarding measurement methods (i.e. any assessment with more or less sensitive method than the one used to assess the lesion at baseline is considered UNK) and not available evaluations (i.e. if any target or non-target lesion was not evaluated the whole overall lesion response is UNK unless remaining lesions qualified for PD). This contrasts with the slightly more flexible guidance given to local investigators (and to the central reviewers) to use expert judgment in determining response in these type of situations, and therefore as a consequence discrepancies between the different sources of response assessment often arise. To ensure the quality of response assessments from the local site and/or the central reviewer, the responses may be re-evaluated by clinicians (based on local investigator data recorded in eCRF or based on central reviewer data entered in the database) at Novartis or external experts. In addition, data review reports will be available to identify assessments for which the investigators' or central reader's opinion does not match the programmed calculated response based on RECIST criteria. This may be queried for clarification. However, the investigator or central reader's response assessment will never be overruled.

If Novartis elect to invalidate an overall lesion response as evaluated by the investigator or central reader upon internal or external review of the data, the calculated overall lesion response at that specific assessment is to be kept in a dataset. This must be clearly documented in the RAP documentation and agreed before database lock. This dataset should be created and stored as part of the 'raw' data.

Any discontinuation due to 'Disease progression' without documentation of progression by RECIST criteria should be carefully reviewed. Only subjects with documented deterioration of symptoms indicative of progression of disease should have this reason for discontinuation of treatment or study evaluation.

16.3.4.5 Programming rules

The following should be used for programming of efficacy results:

16.3.4.5.1 Calculation of 'time to event' variables

Time to event = end date - start date + 1 (in days)

When no post-baseline tumor assessments are available, the date of randomization/start of treatment will be used as end date (duration = 1 day) when time is to be censored at last tumor assessment, i.e. time to event variables can never be negative.

16.3.4.5.2 Incomplete assessment dates

All investigation dates (e.g. X-ray, CT scan) must be completed with day, month and year.

If one or more investigation dates are incomplete but other investigation dates are available, this/these incomplete date(s) are not considered for calculation of the assessment date (and

assessment date is calculated as outlined in [Section 16.3.3.2.8](#)). If all measurement dates have no day recorded, the 1st of the month is used.

If the month is not completed, for any of the investigations, the respective assessment will be considered to be at the date which is exactly between previous and following assessment. If a previous and following assessment is not available, this assessment will not be used for any calculation.

16.3.4.5.3 Incomplete dates for last known date patient alive or death

All dates must be completed with day, month and year. If the day is missing, the 15th of the month will be used for incomplete death dates or dates of last contact.

16.3.4.5.4 Non-target lesion response

If no non-target lesions are identified at baseline (and therefore not followed throughout the study), the non-target lesion response at each assessment will be considered ‘not applicable (NA)’.

16.3.4.5.5 Study / project specific programming

The standard analysis programs need to be adapted for each study/project.

16.3.4.5.6 Censoring reason

In order to summarize the various reasons for censoring, the following categories will be calculated for each time to event variable based on the treatment completion page, the study evaluation completion page and the survival page.

For survival the following censoring reasons are possible:

- Alive
- Lost to follow-up

For PFS and TTP (and therefore duration of responses) the following censoring reasons are possible:

- Ongoing without event
- Lost to follow-up
- Withdraw consent
- Adequate assessment no longer available*
- Event documented after two or more missing tumor assessments (optional, see [Table 16-7](#))
- Death due to reason other than underlying cancer (*only used for TTP and duration of response*)
- Initiation of new anti-cancer therapy

* Adequate assessment is defined in [Section 16.3.3.2.8](#). This reason is applicable when adequate evaluations are missing for a specified period prior to data cut-off (or prior to any other censoring reason) corresponding to the unavailability of two or more planned tumor assessments prior to the cut-off date. The following clarifications concerning this reason should also be noted:

- This may be when there has been a definite decision to stop evaluation (e.g. reason "Sponsor decision" on study evaluation completion page), when subjects are not followed for progression after treatment completion or when only UNK assessments are available just prior to data cut-off).
- The reason "Adequate assessment no longer available" also prevails in situations when another censoring reason (e.g. withdrawal of consent, loss to follow-up or alternative anti-cancer therapy) has occurred more than the specified period following the last adequate assessment.
- This reason will also be used to censor in case of no baseline assessment.

16.4 Appendix 4: NSCLC staging according to AJCC 8th edition

Figure 16-1 NSCLC staging: AJCC 8th edition

T/M	Subcategory	N0	N1	N2	N3
T1	T1a	IA1	IIB	IIIA	IIIB
	T1b	IA2	IIB	IIIA	IIIB
	T1c	IA3	IIB	IIIA	IIIB
T2	T2a	IB	IIB	IIIA	IIIB
	T2b	IIA	IIB	IIIA	IIIB
T3	T3	IIB	IIIA	IIIB	IIIC
T4	T4	IIIA	IIIA	IIIB	IIIC
M1	M1a	IVA	IVA	IVA	IVA
	M1b	IVA	IVA	IVA	IVA
	M1c	IVB	IVB	IVB	IVB

Note:

Subjects with histological stage within the red box will be eligible.

N2, T4 and N2+ T4 subjects are not eligible.

## Template Document History – Changes compared to previous version

Date	Version number	Summary of changes
15-Oct-2019	1.0	N/A
28-Apr-2020	2.0	
The main rationale for SAP Amendment 1 is:
 

• To implement the request from the Health Authority to modify the target population for both the primary and secondary endpoint of Major Pathological Response (MPR) in all three treatment arms from “evaluable subjects” to “randomized subjects” as implemented in the protocol amendment V01.

• The statistical assumptions for the target MPR rate for the combination arm was updated to 45% which is a 25% absolute improvement to account for the change of analysis population from evaluable subjects to randomized subjects.

  

• Specify the analyses to assess the relationship between key blood or tissue based biomarkers and MPR

20-June-2022	3.0	
The main changes in SAP Amendment 2 are:
 

• Added wordings in Section 1 to document recruitment halt

• Included estimand language in Section 1.2 as per new SAP template

• Updated the definition of date of last exposure to study drug/treatment to take into account the patients' withdrawal of consent in Section 2.1.3.6

• Updated the definition of on-treatment period and post-treatment period in Section 2.1.3.10

• Implemented the summaries about COVID-19 related protocol deviations in Section 2.3

• Removed the wording “antineoplastic surgery will be coded using MedDRA” in Section 2.4.2

• In Section 2.5.2 added “or has the surgery performed but with unevaluable MPR result” in the primary variable of primary estimand. Clarified that posterior distribution will be based on data from subjects in the

Date	Version number	Summary of changes
		
FAS. Provided more details about the analysis supporting primary endpoint
 

• Updated the prior distribution in Section 2.5.2, 2.6.1 and 5.4.1, to reflect the change of the MPR rate in the canakinumab in combination with pembrolizumab arm, from “50% in the evaluable patients” to “45% in the randomized patients”.

■ [REDACTED]

• Removed listings of all biomarker data in Section 2.10

• Updated the true MPR rate in Table 3-2

• In Section 5.4.1 removed SAS code and added explanation about how confidence interval for MPR and MPR difference will be obtained in SAS. Updated true MPR value. Removed "evaluable"

## List of abbreviations

ADA	Anti-drug antibodies
AE	Adverse event
AESI	Adverse event of special interest
ATC	Anatomical Therapeutic Classification
BMI	Body Mass Index
BOR	Best Overall Response
CSR	Clinical Study report
CTC	Common Toxicity Criteria
CTCAE	Common Terminology Criteria for Adverse Events
DAR	Dose Administration Record
DI	Dose Intensity
DRL	Drug Reference Listing
ECG	Electrocardiogram
ECOG	Eastern Cooperative Oncology Group
eCRF	Electronic Case Report Form
FAS	Full Analysis Set
i.v.	Intravenous
MedDRA	Medical Dictionary for Regulatory Activities
MPR	Major Pathological Response
NCI	National Cancer Institute
ORR	Overall Response Rate
PAS	Pharmacokinetic Analysis Set
PDI	Planned Dose Intensity
PK	Pharmacokinetics
Q3W	Every 3 Week
RDI	Relative Dose Intensity
RECIST	Response Evaluation Criteria in Solid Tumors
SAP	Statistical Analysis Plan
s.c.	Subcutaneous
SOC	System Organ Class
TFLs	Tables, Figures, Listings
WHO	World Health Organization
WHO-DD	World Health Organization-Drug Dictionary

## **1 Introduction**

This statistical analysis plan (SAP) describes the planned analyses for the primary clinical study report (CSR) of study CACZ885V2201C, a randomized, open-label, phase II study of canakinumab or pembrolizumab as monotherapy or in combination as neoadjuvant therapy in subjects with resectable non-small cell lung cancer.

As specified in the [Section 3](#) of study protocol, the primary analysis will be performed after all subjects have had surgical resection or have discontinued study treatment earlier due to any reason. At this time, the CSR for primary analysis will be produced. On Feb. 1, 2022, Novartis decided to halt the recruitment into the study given the number of subjects already randomized to the study and the challenges with recruitment.

No change was made to the statistical assumptions and the impact on the probability of declaring proof of efficacy (power) and the probability of missing proof of efficacy (type I error rate) will be limited. The primary analysis will be conducted as planned according to the protocol.

The content of this SAP is based on protocol CACZ885V2201C version 01 (dated 07-Apr-2020). All decisions regarding the primary analysis, as defined in the SAP document, have been made prior to database lock of the study data.

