12.8 Sample size calculation

12.8.1 Primary endpoint(s)

A MPR of approximately 20% can be achieved using chemotherapy ([Pataer 2012](#)). A 10% absolute improvement to 30% and a 25% absolute improvement to 45% in MPR rate are considered clinically meaningful minimum improvement in canakinumab alone arm and canakinumab in combination with pembrolizumab arm, respectively.

Approximately 110 subjects will be randomized in a 2:2:1 ratio to one of the treatment arms (canakinumab alone or canakinumab in combination with pembrolizumab or pembrolizumab alone). The proof of efficacy in each treatment arm will be determined by Bayesian double criteria.

Among the 44 subjects randomized to canakinumab single agent treatment, at least 14 responders are needed to meet the proof of efficacy criteria. When the true MPR rate is $\leq 20\%$, the probability of erroneously declaring proof of efficacy is at most 4.4%, while the probability of declaring proof of efficacy is at least 89.8% for $\text{MPR} \geq 40\%$ ([Table 12-1](#)).

Among the 44 subjects randomized to the canakinumab and pembrolizumab combination treatment, at least 20 responders are required to meet the proof of efficacy criteria. When the true MPR rate is $\leq 30\%$, the probability of erroneously declaring proof of efficacy is at most 2.1% while the probability of declaring proof of efficacy is at least 92.2% for $\text{MPR} \geq 55\%$ ([Table 12-2](#)). Assuming an enrollment rate of 6 subjects per month, the enrollment will be completed at approximately 18 months and MPR assessment for the last patient randomized will occur at approximately 20 months from the date of first subject randomized in the study.

Table 12-1 Operating characteristics with 44 subjects randomized to canakinumab treatment arm

True MPR	Probability of declaring proof of efficacy (14 or more responders)	Probability of missing proof of efficacy (13 or less responders)
20%	4.4%	95.6%
30%	45.2%	54.8%
40%	89.8%	10.2%
50%	99.5%	0.5%

Table 12-2 Operating characteristics with 44 subjects randomized to the canakinumab + pembrolizumab combination treatment arm

True MPR	Probability of declaring proof of efficacy (20 or more responders)	Probability of missing proof of efficacy (19 or less responders)
30%	2.1%	97.8%
40%	27.7%	72.3%
45%	53.4%	46.6%
55%	92.2%	7.8%

13 Ethical considerations and administrative procedures

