### **1.1 Study design**

[figure not shown]
This is a phase II, randomized, open-label study evaluating efficacy and safety of canakinumab or pembrolizumab monotherapy or in combination as neoadjuvant treatment.

Approximately 110 subjects were planned to be randomized in a 2:2:1 ratio to one of the treatment arms (Canakinumab alone, Canakinumab in combination with Pembrolizumab and Pembrolizumab alone). Subjects randomized will receive two doses of canakinumab (200mg s.c. Q3W) alone or in combination with pembrolizumab or two doses of pembrolizumab as single agent (200mg i.v. Q3W) ([Figure 1-1](#)). Randomization will be stratified by histology (squamous vs non-squamous). Subjects with adenosquamous histology can be stratified as squamous or non-squamous based on the predominant histology.

The primary endpoint is the MPR rate as assessed by the percentage of subjects with  $\leq 10\%$  residual viable cancer cells based on central review. Primary analysis will be performed after all subjects have had surgical resection or have discontinued study treatment earlier due to any reason.

No formal interim efficacy analysis is planned in this study.

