# **3 Sample size calculation**

## **3.1 Primary analysis**

A MPR of approximately 20% can be achieved using chemotherapy (Pataer 2012 et al). A 10% absolute improvement to 30% and a 25% absolute improvement to 45% in MPR rate are considered clinically meaningful minimum improvement in canakinumab alone arm and canakinumab in combination with pembrolizumab arm, respectively.

Approximately 110 subjects will be randomized in a 2:2:1 ratio to one of the treatment arms (canakinumab alone or canakinumab in combination with pembrolizumab or pembrolizumab alone). The proof of efficacy in each treatment arm will be determined by Bayesian double criteria.

Among the 44 subjects randomized to canakinumab single agent treatment, at least 14 responders are needed to meet the proof of efficacy criteria. When the true MPR rate is  $\leq 20\%$ , the probability of erroneously declaring proof of efficacy is at most 4.4%, while the probability of declaring proof of efficacy is at least 89.8% for MPR  $\geq 40\%$  (Table 3-1).

Among the 44 subjects randomized to the canakinumab and pembrolizumab combination treatment, at least 20 responders are required to meet the proof of efficacy criteria. When the true MPR rate is  $\leq 30\%$ , the probability of erroneously declaring proof of efficacy is at most 2.1% while the probability of declaring proof of efficacy is at least 92.2% for MPR  $\geq 55\%$  (Table 3-2). Assuming an enrollment rate of 6 subjects per month, the enrollment will be completed at approximately 18 months and MPR assessment for the last patient randomized will occur at approximately 20 months from the date of first subject randomized in the study.

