**Table 3-1      Operating characteristics with 44 subjects randomized to canakinumab treatment arm**

True MPR	Probability of declaring proof of efficacy (12 or more responders)	Probability of missing proof of efficacy (11 or less responders)
20%	4.4%	95.6%
30%	45.2%	54.8%

True MPR	Probability of declaring proof of efficacy (12 or more responders)	Probability of missing proof of efficacy (11 or less responders)
40%	89.8%	10.2%
50%	99.5%	0.5%

**Table 3-2 Operating characteristics with 44 subjects randomized to the canakinumab + pembrolizumab combination treatment arm**

True MPR	Probability of declaring proof of efficacy (20 or more responders)	Probability of missing proof of efficacy (19 or less responders)
30%	2.1%	97.8%
40%	27.7%	72.3%
45%	53.4%	46.6%
55%	92.2%	7.8%

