### **Calculation of posterior probability**

The criteria for proof of efficacy are:

- the mean of the posterior distribution of MPR is at least 30% and
- the posterior probability that the MPR is  $\geq 20\%$  is at least 90%

for canakinumab single agent arm and

- the mean of the posterior distribution of MPR is at least 45% and

- the posterior probability that the MPR is  $\geq 30\%$  is at least 90% for canakinumab and pembrolizumab combination arm.

Let  $p_1$  denote the MPR rate for canakinumab single agent and follow a beta prior distribution  $\text{Beta}(a_1, b_1)$ , where  $a_1 > 0, b_1 > 0$ . Let  $y_1$  out of  $n_1$  patients reach MPR in canakinumab single agent arm. Then the posterior distribution of  $p_1$  is  $\text{Beta}(a_1 + y_1, b_1 + n_1 - y_1)$  (Spiegelhalter et al. 2004). Similarly, for canakinumab and pembrolizumab combination arm, the posterior distribution of  $p_2$  is  $\text{Beta}(a_2 + y_2, b_2 + n_2 - y_2)$ .

A minimally informative unimodal Beta prior (Neuenschwander et al. 2008) will be used. For canakinumab single agent arm, the parameters will be chosen so that the mean of the prior distribution is equal to 0.3, which corresponds to  $\text{Beta}(3/7, 1)$ . For canakinumab in combination with pembrolizumab arm, the parameters will be chosen so that the median of the prior distribution is equal to 0.45, which corresponds to  $\text{Beta}(9/11, 1)$ .

The efficacy criteria will be assessed based on the actual number of patients enrolled. For example, if the total number of patients in canakinumab is 44, the first efficacy criterion requires that at least 14 patients who are MPR responders. In that case, the posterior distribution is  $\text{Beta}(3/7 + 14, 1 + 44 - 14)$  and the posterior probability  $P(\text{MPR rate} \geq 0.2) = 96.5\%$ .

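### After the recruitment halt, the SAP gives its error statement the wrong label and no calculation; error rates exist only for 44 per arm, under a Table 3-1 header with the wrong responder threshold

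*SAP*

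**What the plan says.** SAP section 1 records the halt, says no statistical assumption was changed, and describes the effect on two probabilities as small. It labels the first, declaring proof of efficacy, as power. Of the second it says "the probability of missing proof of efficacy (type I error rate) will be limited". It gives neither the number randomised per arm nor a calculation.

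Section 1.1 keeps the original target: "Approximately 110 subjects were planned to be randomized in a 2:2:1 ratio", which is 44:44:22. Section 3.1 and Tables 3-1 and 3-2 give operating characteristics for 44 per canakinumab-containing arm only. For canakinumab alone, section 3.1 says "at least 14 responders are needed to meet the proof of efficacy criteria" and that "the probability of erroneously declaring proof of efficacy is at most 4.4"%. For the combination, with 20 responders required, it says "the probability of erroneously declaring proof of efficacy is at most 2.1"%.

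The header of SAP Table 3-1 reads "Probability of declaring proof of efficacy (12 or more responders"), whereas protocol Table 12-1, with the same four probabilities, reads "Probability of declaring proof of efficacy (14 or more responders").

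Section 5.4.1 states: "The efficacy criteria will be assessed based on the actual number of patients enrolled".

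**The concern.** In the section 1 sentence the description and the label belong to different errors. In Tables 3-1 and 3-2, missing proof of efficacy is the complement of declaring it, so when the drug works it is the type II error. The type I error is the one section 3.1 describes, a declaration made in error. If the description was meant, the sentence mentions power twice and says nothing about false positives. If the label was meant, false positives are called limited with nothing behind it.

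This matters because the rule is applied at the achieved arm size and its integer responder threshold moves with that size. Anyone weighing a positive result after the halt needs the false-positive rate and power at that size. The only figures to fall back on are those for 44, and they carry a wrong threshold in one header and a wrong last digit in one rate.

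**Working it through.** **Inputs.** Criteria and priors are from SAP 2.5.2 and 5.4.1.
- Canakinumab alone: prior Beta(3/7, 1); posterior mean at least 30% and P(MPR ≥ 20%) at least 90%.
- Combination: prior Beta(9/11, 1); posterior mean at least 45% and P(MPR ≥ 30%) at least 90%.

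**Formulas.** With y responders of n and prior Beta(a, 1), the posterior is Beta(a + y, 1 + n − y), with mean (a + y)/(a + 1 + n). The threshold r is the smallest y meeting both criteria. The probability of declaring efficacy is the exact binomial tail P(X ≥ r | n, p).

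**Step 1: threshold for canakinumab alone at n = 44.** The mean is (3/7 + y)/(10/7 + 44).

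| Responders | Posterior mean | P(MPR ≥ 20%) | Both met? |
|---|---|---|---|
| 12 | 27.4% | 87.2% | No, both fail |
| 13 | 29.6% | 93.0% | No, mean fails |
| 14 | 31.8% | 96.5% | Yes |

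So r = 14, as in SAP 3.1, and 96.5% agrees with the worked example in 5.4.1.

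**Step 2: reproduce Table 3-1 (n = 44).**

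| True MPR | Printed | P(X ≥ 14) | P(X ≥ 12) |
|---|---|---|---|
| 20% | 4.4% | 4.36% | 15.42% |
| 30% | 45.2% | 45.21% | 70.64% |
| 40% | 89.8% | 89.79% | 97.23% |
| 50% | 99.5% | 99.52% | 99.94% |

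The printed figures are those for 14. The header is wrong and the numbers are right.

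**Step 3: reproduce Table 3-2 (n = 44, r = 20).** The exact values at 30/40/45/55% are 2.18%, 27.73%, 53.41% and 92.25%. All agree with print except the first. P(X ≥ 20) is 2.176% and P(X ≤ 19) is 97.82%, so 2.1% should be 2.2%. The table's own pair, 2.1% and 97.8%, sums to 99.9%.

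**Step 4: smaller arms.** The achieved sizes are not in the documents, so n = 36 to 43 is an assumption. The threshold is re-derived at each n.

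| n | Canakinumab r | False positive at 20% | Power at 40% | Combination r | False positive at 30% | Power at 55% |
|---|---|---|---|---|---|---|
| 36 | 11 | 8.89% | 90.96% | 17 | 2.19% | 86.54% |
| 37 | 12 | 5.17% | 86.67% | 17 | 2.95% | 89.81% |
| 38 | 12 | 6.23% | 89.11% | 18 | 1.80% | 86.61% |
| 39 | 12 | 7.42% | 91.18% | 18 | 2.42% | 89.79% |
| 40 | 12 | 8.75% | 92.91% | 18 | 3.20% | 92.33% |
| 41 | 13 | 5.21% | 89.45% | 19 | 1.99% | 89.79% |
| 42 | 13 | 6.21% | 91.40% | 19 | 2.64% | 92.28% |
| 43 | 13 | 7.33% | 93.05% | 20 | 1.64% | 89.80% |
| 44 | 14 | 4.36% | 89.79% | 20 | 2.18% | 92.25% |

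For the combination at n = 40, 18 responders give (9/11 + 18)/(20/11 + 40) = 207/460 = 0.45 exactly, which satisfies a criterion of at least 45%. A program using floating-point arithmetic can miss this tie and require 19.

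**Step 5: separate the shortfall from the integer threshold.** For canakinumab alone, n = 45 gives 5.21% and n = 46 gives 6.15% (r = 14 for both), so 4.4% is a low point of a saw-tooth. Averaging over whole threshold cycles removes most of that effect:
- one cycle each: 6.25% for n = 41–43 against 5.24% for n = 44–46, a difference of 1.0 point;
- two cycles each: 6.62% for n = 37–43 against 5.00% for n = 44–50, a difference of 1.6 points.

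**The case against.** The strongest reply is that nothing in the analysis is undefined. Section 5.4.1 already applies the criteria at the actual enrolment, and efficacy is declared from the posterior, never from a table header. Section 3.1, the example in 5.4.1 and protocol Table 12-1 all use 14, so few readers would act on 12. That stands: these are errors in the reported operating characteristics, not in the rule.

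A second reply is that the figures largely fit the word limited. Power moves by a few points, and combination false positives go both ways around 2.2%. No document sets a type I ceiling; 4.4% describes the rule at n = 44. This also stands, and it is why the claim is not called false. It does not cover canakinumab alone, where the false-positive rate exceeds 4.4% at every n from 36 to 43.

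A third reply is that the size rests on assumed arm sizes, and that comparing averages is a rough way to isolate the effect of the halt. The first half is correct, and the missing arm sizes are part of the gap. On the second, the 1.0 and 1.6 points come from whole threshold cycles, so they are not produced by choosing favourable end points. They remain averages and do not predict the result at one particular n.

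The 2.1% slip is small and predates the halt, since protocol 12.8.1 has it too. It is included because the text presents it as an upper bound and the exact value exceeds it.

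**Conclusion.** The concern holds. Three things are wrong as written: the error label in SAP section 1, the responder threshold in the SAP Table 3-1 header (12, should be 14), and the combination false-positive rate (2.1%, should be 2.2%). One thing is missing: any calculation behind the statement that the halt has limited impact.

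Assuming 36 to 43 per arm, canakinumab false positives at 20% are 5.2% to 8.9% against 4.4% at 44. The shortfall itself accounts for roughly 1 to 2 points on average and the integer threshold for the rest. Combination false positives at 30% are 1.6% to 3.2% against 2.2%. Power is 87% to 93% for canakinumab at 40% and 87% to 92% for the combination at 55%. Limited is therefore reasonable for power over this range and unsupported for canakinumab false positives. The reproduction at n = 44 needs no assumption; everything at other sizes depends on the assumed n.

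**What to change.** 1. In SAP section 1, name both errors correctly (erroneous declaration as type I, missed efficacy as type II) and address each.
2. Replace the unsupported statement with a short table at the number actually randomised to each arm: responder threshold, exact false-positive rate at 20% (canakinumab) and 30% (combination), and probability of success at 40% and 55%. Compute the posterior-mean criterion in exact arithmetic so that ties such as 18 of 40 are handled correctly.
3. Keep the n = 44 figures, marked as planning values. Change the SAP Table 3-1 headers to 14 or more and 13 or less.
4. Change 2.1% to 2.2% in the SAP 3.1 text and Table 3-2, and note the same correction for protocol 12.8.1 and Table 12-2.

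The cost is one sentence, one small table, one pair of column headers and one percentage. No analysis, prior or decision rule changes. The one drawback for the sponsor is that the stated canakinumab false-positive rate may come out less favourable than 4.4%.
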